## 7.7. Concomitant therapy

Administration of concomitant medications/therapies to the patient during the study period must be reported on the concomitant medications page of the eCRF. A medication or therapy is defined as concomitant when administered between the date of signature of informed consent and end of study (EOS). Information to be reported on the eCRF includes: i) international non-proprietary name and trade name, ii) dosage information (dose, unit, frequency, route), iii) dates of administration, and iv) reasons for use.

### 7.7.1. Permitted medications

Permitted medications are:

- Supportive therapies to treat any emergent serious condition notably including medications against pain, nausea, vomiting, and diarrhea (per the Investigator's decision).
- Granulocyte colony-stimulating factor (G-CSF) and erythropoietic agents (per the Investigator's decision).
- Transfusions and blood-derived products as per local institutional guidelines.
- Bisphosphonates or denosumab as per local institutional guidelines in patients with symptomatic bone metastases, or malignant hypercalcemia or with increased risk of bone fractures.
- Steroids or anti-histaminic drugs according to local institutional standard protocols or guidelines (if any) for allergic reactions Grade  $\geq 2$  or prophylactically after C1D1.
- Patients requiring prolonged systemic steroids administration for any emerging medical cause at doses in excess of physiological replacement doses or more than prednisone 10 mg/d, should discontinue study treatment according to risk/benefit evaluation.
- Levetiracetam and pregabalin (per the Investigator's decision).
- Treatment of pain should be done according to severity and recommended drugs. Study-specific guidelines will be available.
- Any other medication for the well-being of the patient except those mentioned as prohibited medications at the Investigator's discretion.
- The use of oral contraceptives should be carefully evaluated during study treatment as well as the use of other drugs reported to cause liver injury.

### 7.7.2. Prohibited medications

Attention should be paid to treatment that could influence the intended effects or mask side effects of study treatment. Use of drugs reported to cause liver injury should be carefully evaluated.

Concomitant use (until the EOT visit) of the following drugs and treatment modalities is prohibited (see [Appendix B: Prohibited medications](#) for the full list), except if they are indicated to treat any TEAEs related to study treatment ([i.e. anti-TNF- $\alpha$  therapy]). In this case, administration of these drugs is allowed and must be documented after interrupting Debio 1143 treatment.

- Strong P-gp inhibitors or inducers (see [Appendix B: Prohibited medications](#))
- Anti-TNF- $\alpha$  therapy (e.g. adalimumab [Humera®], etanercept [Enbrel®], infliximab [Remicade®], etc.)
- Other investigational agents other than mAbs within a 2-week period prior to initial dosing or while receiving Debio 1143
- Systemic corticosteroids, exceeding 10 mg/d of prednisolone or equivalent or physiological replacement doses of hydrocortisone. Note: topical corticosteroids for any indication, megestrol, or inhaled corticosteroids for reactive airway disease are permitted.

- Alcohol dependency defined as drinking greater than 100/140g (3.5/4.9 ounces) of alcohol per week for female/male patients, respectively
- Grapefruit juice or grapefruit-containing products and St John's Wort containing products
- Narrow therapeutic range or sensitive CYP 3A substrates or other drugs on the prohibited medication list (see [Appendix B: Prohibited medications](#)).

Restrictions also apply for P-gp substrates during Debio 1143 on-treatment periods (see [Appendix B: Prohibited medications](#)). In addition, narrow therapeutic range or sensitive CYP 2Cs (2C8, 2C9, 2C19), 2B6 or 1A2 substrates should be closely monitored. A list of drugs that are sensitive substrates of CYPs is available from website resources such as: Flockhart DA. Drug Interactions: Cytochrome P450 Drug Interaction Table. Indiana University School of Medicine (2007); <http://medicine.iupui.edu/clinpharm/ddis/table.aspx>.

Finally, considering that the potential of Debio 1143 to prolong the QTc interval has not yet been fully characterized, caution should be exercised when using Debio 1143 with drugs having a known risk of QTc prolongation (refer to product label or Arizona CERT database at website: <http://www.crediblemeds.org>). Monitoring of patients' electrolyte levels is strongly recommended.

### 7.7.3. Contraceptive measures

Based on its mechanism of action and data from animal studies, it is known that nivolumab can cause fetal harm when administered to a pregnant woman. In animal reproduction studies, administration of nivolumab to cynomolgus monkeys from the onset of organogenesis through delivery resulted in increased abortion and premature infant death. Human IgG4 is known to cross the placental barrier. Nivolumab therefore has the potential to be transmitted from the mother to the developing fetus, with greater effects during the second and third trimesters of pregnancy. Nivolumab is not recommended during pregnancy and in women of childbearing potential (WOCBP) not using effective contraception.(12)

Animal reproductive studies have not been conducted with Debio 1143. Therefore, it is not known if Debio 1143 or its metabolites are excreted in milk or can cross the placenta. Thus, pregnant or nursing women should not receive Debio 1143. Women of childbearing potential and their partners who are included in a clinical trial of Debio 1143 must take adequate contraceptive measures.

WOCBP patients and male patients, whose partners are WOCBP, enrolled in this clinical trial must take adequate contraceptive measures through defined periods during and after study treatment as specified below.

WOCBP patients and male patients whose partners are WOCBP must:

- Agree to use one highly effective method of contraception as described below. Contraception will be required from study entry up to 5 months after the last day of study treatment, or
- Agree to practice complete sexual abstinence, when this is in line with the preferred and usual lifestyle of the patient (note: periodic abstinence [e.g., calendar, ovulation, symptothermal post-ovulation methods] and withdrawal are not acceptable methods of contraception) from study entry up to 5 months after the last day of study treatment.

Highly effective methods of birth control include:

- Intrauterine device (IUD).
- Intrauterine hormone-releasing system (IUS).
- Combined (estrogen and progesterone containing) hormonal contraception associated with inhibition of ovulation (oral, intravaginal, transdermal)\*.

- Progesterone-only hormonal contraception associated with inhibition of ovulation (oral, injectable, implantable)\*.
- Bilateral tubal ligation.
- Vasectomized partner.
- Double barrier methods (not highly effective, but acceptable)

\*Note: If hormonal contraception is chosen, the use of a barrier method (preferably male condom) is mandatory due to potential risk of CYP 3A4/5 induction by Debio 1143 that may reduce hormonal contraception efficacy.

WOCBP are non-surgically sterile women whose date of last menstruation is within 12 months before the date of the screening visit.

## 8. STUDY ENDPOINTS, ASSESSMENTS, AND PROCEDURES

### 8.1. Endpoints

#### 8.1.1. Primary endpoints

##### 8.1.1.1. Part A

The primary endpoint of part A is the RP2D of Debio 1143 when combined with the standard dose of nivolumab, in patients with advanced solid malignancies who received prior systemic standard treatment and failed a prior PD-1/PD-L1-containing treatment, as per DLT occurrence in less than one-third of evaluable treated patients at the RP2D dose level.

##### 8.1.1.2. Part B

The primary endpoint of part B is the confirmed ORR as per RECIST v1.1 and/or GCIG criteria (Cohort 4, if applicable).

#### 8.1.2. Secondary endpoints

Secondary endpoints for both study parts (unless otherwise specified) are:

- Incidence and severity of TEAEs and clinical laboratory abnormalities, according to NCI-CTCAE version 5.0 criteria
- Changes in vital signs: systolic/diastolic blood pressure, heart rate (both after at least 5 minutes of supine rest), temperature, and weight; ECG and ECOG-PS
- Incidence of premature treatment discontinuations and treatment modifications due to AEs and laboratory abnormalities (i.e., treatment compliance)
- Tumor response determined according to RECIST v1.1 and/or GCIG criteria (Cohort 4, if applicable):
  - Confirmed (Part A) and unconfirmed (Parts A and B) ORR
  - Disease control rate (DCR), defined as any response, partial or complete (PR or CR) + stable disease (SD)
  - Time-related endpoints as median time to response, median DOR, median PFS, PFS rate at 6, 12 and 18 months, median OS, OS rate at 12 months and 18 months (if data allow)

- PK parameters of Debio 1143 and Debio 1143-MET1 as defined in the available population PK model (36) and, if appropriate, post-hoc estimates of areas under the curve (AUCs),  $C_{max}$ , and  $C_{min}$ ; serum concentration versus time profiles of nivolumab and, if deemed appropriate, relevant nivolumab PK parameters derived from a population PK model. (37)

### 8.1.3. Exploratory endpoints

Exploratory endpoints are:

- Potential predictive and PDy biomarkers of Debio 1143 combined with nivolumab, in blood and tumor tissue [REDACTED]
- Best overall response (BOR) evaluation using the novel iRECIST 2017 guideline for immunotherapeutics
- Correlations between PK disposition of Debio 1143 combined with nivolumab and clinical response and/or any tumor metrics
- Correlations between PK disposition of Debio 1143 combined with nivolumab and safety profile, and PDy if applicable
- Correlations between Debio 1143 and Debio 1143-MET1 plasma concentrations and changes from baseline QTcF.
- Correlations between response, clinical parameters, immune correlates and putative biomarkers, [REDACTED]
- Genetic variations in DMET genes associated with differences in the PK disposition of Debio 1143 in combination with nivolumab.

## 8.2. Study assessments

### 8.2.1. Efficacy

Tumors will be assessed according to either RECIST version 1.1 guidelines by CT scan or MRI imaging of the target/non target lesions (38), and/or GCIG criteria using the serum marker CA-125 for Cohort 4, if applicable.(39)

CT scan and MRI will be performed at screening, then every 8 weeks ( $\pm$  1-week tolerance window) during the first 10 cycles, then every 12 weeks ( $\pm$  1 week) from Cycle 13 until symptomatic PD or confirmed iRECIST PD or start of any new cancer treatment or end-of-life care or end of the Main study period, whichever occurs first. For patients who exceptionally continue study treatment after completion of 13 cycles, tumor response assessments will continue at 12-week intervals ( $\pm$  1 week window) until the end of the Main study period, and thereafter at the frequency of local institutional care practice until PD, start of any new anticancer therapy, death or EOT.

Imaging will be performed as per site standard but whenever possible using contrast agent at screening and during treatment

CA-125 dosages will be performed at screening exclusively in patients included in Cohort 4. In case of abnormally elevated levels before treatment start, these dosages will be repeated on Day 1 of each subsequent cycle.

In case of response, efficacy assessments will be repeated 4 weeks later after first documentation (+ 1-week tolerance window). All patients will have an efficacy assessment (CT scan/MRI or serum CA-125 dosage) at the time of disease progression and/or treatment discontinuation, whichever occurs first.

As an exploratory analysis, tumor response will also be assessed using the iRECIST criteria (novel modified RECIST v1.1 guideline for immunotherapeutics).(40) These exploratory analyses will be described in the SAP.

Patients with asymptomatic, but radiologically observed unconfirmed PD as per iRECIST, may continue the study treatment, upon both the Investigator's request and the Sponsor's agreement, until PD is confirmed as per iRECIST or symptoms occurs or Investigator/patient decision to withdraw treatment, whichever occurs first.

### 8.2.1.1. Measurability of tumor lesions

Patients must have at least one measurable tumor lesion, according to the RECIST version 1.1 criteria (38) and/or GCIG criteria (Cohort 4), if applicable.(39)

As per RECIST v1.1 guidelines, measurable tumor lesions must be measured in at least one dimension (longest diameter in the plane of measurement is to be recorded except for measurable lymph nodes) with a minimum size of:

- 10 mm by CT scan (slice thickness  $\leq 5$  mm)
- 10 mm caliper measurement by clinical exam (lesions which cannot be accurately measured with calipers should be recorded as non measurable)
- 20 mm by chest X-ray
- Malignant lymph nodes:  $\geq 15$  mm in short axis when assessed by CT scan (slice thickness  $\leq 5$  mm). Only the short axis is measured.

As per GCIG criteria (Cohort 4, if applicable), patients can be evaluated according to CA-125 only if they have a pretreatment sample that is at least twice the upper limit of the reference range and within 2 weeks before starting the treatment.

### 8.2.1.2. Methods of tumor assessment

The choice of the imaging method for tumor assessment is taken by the site, based on local feasibility and clinical adequacy. However, the same method of assessment and the same technique must be used throughout the trial for any given patient. Extent of disease evaluation by institutional guidelines per RECIST includes CT scan with IV contrast of the thorax, abdomen, and pelvis as well as other anatomical areas as appropriate (i.e., CNS imaging for symptomatic SCLC patients, if appropriate). Of note, all known or suspected disease-involved areas assessed at screening should be at least, included in all subsequent assessments. MRI may be used to assess sites of disease not adequately imaged by CT or in patients known to have an allergy to iodine-containing contrast or moderate to severe renal impairment (calculated creatinine clearance  $< 50$  ml/min).

For Cohort 4 exclusively, extent of disease evaluation by the GCIG criteria includes a monthly dosage of the serum tumor marker CA-125, if applicable, in patients without RECIST measurable disease in ovarian cancer, fallopian cancer, PPC, and/or endometrial cancer with elevated CA-125.

### 8.2.1.3. Tumor response criteria

For the evaluation of target lesions by the RECIST v1.1 criteria, following definitions will be applied (38):

- **CR:** Disappearance of all target lesions. Any pathological lymph nodes must have reduction in short axis to  $< 10$  mm. CR must be confirmed by repeat assessments performed no less than 28 days after the criteria for response are first met to qualify as CR.
- **PR:** At least a 30% decrease in the sum of diameters of target lesions taking as reference the baseline sum diameter. PR must be confirmed by repeat assessments performed no less than 28 days after the criteria for response are first met to qualify as PR.

- **Progressive Disease (PD):** At least a 20% increase in the sum of diameters of target lesions, taking as reference the smallest sum on study (this includes the baseline sum if that is the smallest on study). In addition to the relative increase of 20%, the sum must also demonstrate an absolute increase of at least 5 mm. Note: the appearance of one or more new lesions is also considered progression.
- **Stable Disease (SD):** Neither sufficient shrinkage to qualify for PR, nor sufficient increase to qualify for disease progression, taking as reference the smallest sum diameter while on study.

As per the GCIG criteria (Cohort 4, if applicable), a CA-125 response is defined as at least a 50% reduction in CA-125 levels from a pretreatment sample for patients whose CA-125 level was greater than twice the upper limit of the reference range when they started treatment.

Progressive disease definitions are provided in [Appendix C: Response to treatment criteria](#).

### 8.2.2. Safety

Safety assessments will include vital sign measurements, physical examination findings, clinical laboratory results, ECOG-PS, ECGs, AE monitoring, and concomitant medications. The schedule of assessments is presented in [Table 8-6](#).

#### 8.2.2.1. Adverse events and concomitant medications

AEs will be monitored and recorded throughout the study, from the time the informed consent form (ICF) is signed until up to 5 months after last nivolumab administration provided no new anti-cancer or end-of-life care was started earlier. Ideally an EOT visit should be planned immediately before whenever is feasible.

AEs will be graded according to NCI-CTCAE version 5.0 (see [section 9](#)).

Concomitant medications and procedures, including blood transfusions, will be recorded from signing informed consent through EOS. Alternative cancer therapies will also be recorded during OS follow-up.

#### 8.2.2.2. Physical examination, ECOG score, and vital signs

A complete physical examination will be performed at screening, on Days 1 and 15 of the first three cycles, and then on Day 1 of remaining cycles and at EOT. The ECOG-PS will always be measured along with vital signs comprising systolic/diastolic blood pressure, heart rate (both after at least 5 minutes of supine rest), temperature, and weight at screening, on Days 1, 8, 15, and 22 of Cycle 1, and on Days 1 and 15 of other cycles and at EOT. Height will be recorded only at screening. On dosing days, all assessments should be performed predose.

#### 8.2.2.4. 12-lead ECG

High-quality, digital triplicate 12-lead ECGs will be recorded after 10 minutes of supine rest at screening. High-quality, digital triplicate 12-lead ECGs will be recorded after 10 minutes of supine rest on Day 1 of Cycle 1 and Cycle 3 and on Days 8, 15 and 22 of Cycle 1 at the following 3 time points: pre-, 0.5-2h Debio 1143 post-dose (before starting the nivolumab infusion or after nivolumab perfusion was removed) and 4-6 h post-dose. ECG readings must be performed prior to PK/PDy sampling. There should be at least 1 minute between each ECG and all 3 ECGs should be completed within 10 minutes. Reading will be done centrally by a dedicated team. For eligibility purposes, the screening reading will be done also locally by the investigator or a cardiologist will be consulted if clinically indicated.

#### 8.2.2.5. Safety laboratory

Safety laboratory measurements are scheduled at screening, C1D1 pre-treatment (only required if screening test were performed > 7 days prior to C1D1 or if inclusion/exclusion criteria were not met during screening),

on Days 3 (Part A only), 8, 15, 17 (Part A only), and 22 of Cycle 1, on Days 1 and 15 of Cycle 2 and 3, on Days 1 of any other subsequent cycle and at EOT. On dosing days, samples will always be collected predose and results reviewed prior to nivolumab infusion, if applicable. All measurements will be performed locally.

On Days 3 and 17 of Cycle 1 for patients included in Part A only, serum will be collected and measured for total bilirubin (if >ULN: direct bilirubin should also be measured), alkaline phosphatase (ALP), AST, ALT and creatinine.

For all other visits mentioned above, blood/serum will be measured for the following panels:

- **Hematology:** Hemoglobin, hematocrit, complete blood count (incl. differential) and platelets
- **Chemistry:** Creatinine, sodium, potassium, calcium, total bilirubin (if >ULN: direct bilirubin should also be measured), ALP, AST, ALT, amylase, lipase, lactate dehydrogenase (LDH), total protein, albumin and C-reactive protein (CRP)

In addition, the following laboratory measurements will be collected:

- on Days 1 and 15 of Cycle 1 and Days 1 of each subsequent cycle:

TSH, free triiodothyronine (FT3), free thyroxine (FT4),

- At screening, the following will also be measured: HIV, HBV, and HCV serology, CPK and troponins, FSH/LH and total testosterone (in males) or estrogens (in pre-menopausal female patients, meaning those whose last menstruation occurred within 12 months of screening date), free-cortisol (at morning) and ACTH. These dosages could be repeated if clinically indicated.

For applicable patients included in Cohort 4, CA-125 dosages will be performed at screening within 4 weeks of C1D1 and will be repeated on Day 1 of each subsequent cycle, if abnormally elevated levels are obtained before treatment start. Patients are evaluable as per GCIG criteria only if they have a pretreatment sample that is at least twice the upper limit of the reference range and within 2 weeks before starting the treatment.

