- 1 Digital triplicate 12-lead ECGs will be recorded after 10 minutes of supine rest at the following 3 time points: pre-, 0.5-2h Debio 1143 post-dose (before starting the nivolumab infusion or after nivolumab perfusion was removed) and 4-6 h post-dose; There should be at least 1 minute between each ECG and all 3 ECGs should be completed within 10 minutes or less. ECG readings must be performed before PK/PDy sampling. ECG reading will be done centrally and also locally for screening purposes.
- 2 Pre-dose (as per section 8.2.2.5) only required if screening test were performed > 7 days prior to C1D1 or if inclusion/exclusion criteria were not met during screening:
- 2a HIV, HCV and HBV serology testing and CPK and Troponins (I or T whichever is applicable): Only at screening, to be repeated if clinically indicated only.
- 2b FSH/LH and total testosterone (in male) or estrogens (in female patients), free-cortisol (at morning) and ACTH: Only at screening and to be repeated if clinically indicated.
- 2c Hemoglobin, hematocrit, platelets and complete blood cell count and differential counts, creatinine, sodium, potassium, calcium, total bilirubin (if >ULN, then also measure direct bilirubin), ALP, AST, ALT, amylase, lipase, LDH, total protein, albumin, CRP.
- 2d Part A patients (only): Total bilirubin (if >ULN, then direct bilirubin should also be measured), ALP, AST, ALT, and creatinine.
- 2e TSH, FT3 and FT4: At Day 1 and Day 15 in Cycle 1 and every Day 1 of each subsequent cycle.
- 2f CA-125 to be performed at screening within 4 weeks of C1D1, exclusively in applicable patients included in Cohort 4, and to be repeated before start of each new cycle if abnormally elevated before treatment start, unless PD, any new anticancer treatment or end-of-life hospice care is started before.
- 3 In women of childbearing potential only: blood test at screening (only required if screening test were performed > 7 days prior to C1D1), then urine dipstick test alone would be sufficient, at the beginning of each treatment cycle while on study up to 5 months after EOT.

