### 9.1.6. Adverse events of special interest

AESIs are

1. for Debio 1143:
  - a. AST or ALT increases >3 ULN associated with total bilirubin >2 ULN and ALP <2 ULN
  - b. Lipase or amylase increases >5 ULN
  - c. Any QTcF prolongation above 30 ms compared to baseline on at least two consecutive readings or other ECG abnormalities such as Torsade de Pointe, ventricular tachycardia, ventricular fibrillation, flutter or any other new cardiac abnormality at the ECG or during the physical examination considered as clinically significant.
2. for nivolumab:
  - a. Any AEs that are suspected to be immune-related or infusion-related including drug hypersensitivity, immune-related pneumonitis, immune-related colitis, immune-related hepatitis, immune-related endocrinopathies such as: thyroid disorders, adrenal insufficiency, new onset type I diabetes mellitus, pituitary disorders; or immune-related

nephritis and renal dysfunction and other immune-related AEs such as: myositis, myocarditis, Guillain-Barré syndrome or uveitis of any grade

All AESIs, occurring after treatment start on C1D1 must be reported to the sponsor in the appropriate eCRF pages. When reporting these cases, it has to be specified in the eCRF whether the case is serious or non-serious. If the AESI(s) is/are serious or considered to be a DLT, then it has to be properly reported within 24 hours of acknowledgement and all applicable SAEs reporting guidelines should be followed (as described in [section 9.2](#)) including the reason why it is considered serious.

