18.3. LABORATORY EVALUATIONS

Results from the laboratory will be included in the reporting of this study for Haematology, Chemistry, Virology and Endocrinology. A list of laboratory assessments to be included in the outputs is included in the protocol (section 8.2.2.4 and as a footnote to table 8-6: schedule of assessments).

Presentations will use SI Units.

Quantitative laboratory measurements reported as “< LLOQ”, i.e. below the lower limit of quantification (BLQ), or “>ULOQ”, i.e. above the upper limit of quantification (ULQ), will be converted to the lower limit of quantification (LLOQ) or the upper limit of quantification (ULOQ) for the purpose of quantitative summaries, but will be presented as recorded, i.e. as “< LLOQ” or “>ULOQ” in the listings.

The following summaries will be provided for each lab parameter:

- Actual and change from baseline by visit (for quantitative measurements)
- Worst on-treatment CTCAE grade for each gradable parameter

Document: T:\sas\Debiopharm\Debio_1143\CZA60507\Biostatistics\Documentation\SAP\SAP Text\V5

Author: XXXXXXXXXX Version Number: 5.0
Version Date: 19APR2022

Template No.: CS_TP_BS016 Revision 5
Effective Date: 01Apr2018

Reference: CS_WI_BS005

Copyright © 2009, 2010, 2012, 2016, 2018 IQVIA. All rights reserved. The contents of this document are confidential and proprietary to IQVIA Holdings Inc. and its subsidiaries. Unauthorized use, disclosure or reproduction is strictly prohibited.

- Shift using CTCAE grades from baseline to the worst on-treatment value
- Shift from baseline to the worst on-treatment value using the low / normal / high / (low and high) classification (only for non-gradable parameters)
- Incidence of maximum grade on treatment presented overall and by cycle, updating denominator for each cycle with the number patients receiving at least one dose of nivolumab in that cycle (only for gradable parameters)
- For patients having a grade 3/4 value:
 - Time to First Grade 3/4 Toxicity and Time to Resolution:
 - Time to recovery to grade ≤ 2
 - Time to recovery to grade ≤ 1
 - Time to full recovery (grade 0)
 - Conservative duration: (first assessment showing improvement (lower than grade 3/4) – date when analyte first graded 3/4 + 1)
 - Non-conservative duration: (last date analyte graded 3/4 (before grade ≤ 2) – date when analyte first graded 3/4 + 1)

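### New-onset type I diabetes is a named AESI, but no glucose, HbA1c or urinalysis is scheduled, so its reported incidence rests on symptoms or unscheduled tests and there is no baseline value

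*Protocol*

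**What the plan says.** - **The event.** Among the nivolumab AESIs, Protocol 9.1.6 lists "immune-related endocrinopathies such as: thyroid disorders, adrenal insufficiency, new onset type I diabetes mellitus, pituitary disorders". The list covers events of any grade. On reporting: "All AESIs, occurring after treatment start on C1D1 must be reported to the sponsor in the appropriate eCRF pages".
- **The chemistry panel.** Protocol 8.2.2.5 sets it out, ending with "ALP, AST, ALT, amylase, lipase, lactate dehydrogenase (LDH), total protein, albumin and C-reactive protein (CRP"), and footnote 2c of Tables 1-1 and 8-6 repeats it: "creatinine, sodium, potassium, calcium, total bilirubin (if >ULN, then also measure direct bilirubin), ALP, AST, ALT, amylase, lipase, LDH, total protein, albumin, CRP". The list is complete and unredacted in all three places.
- **Other endocrine tests.** For the thyroid, footnote 2e gives "TSH, FT3 and FT4: At Day 1 and Day 15 in Cycle 1 and every Day 1 of each subsequent cycle". FSH/LH, sex hormones, morning cortisol and ACTH are taken at screening and repeated only on clinical indication.
- **Urine.** The schedule's note on the order of procedures mentions urine samples, but the only urine test defined is for pregnancy (8.2.2.6).
- **Management.** Table 7-2 separates Grade 1-2 from Grade 3-4 type I diabetes. It says what to do once a case is recognised and schedules no test to find one.
- **Analysis.** SAP 18.3 states: "Results from the laboratory will be included in the reporting of this study for Haematology, Chemistry, Virology and Endocrinology". It takes the analyte list from the protocol. SAP 18.1.16 counts AESIs that the investigator flagged on the eCRF, by SOC/PT with cycle and worst grade.

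**The concern.** The plan commits to counting an event by grade without scheduling the measurement that would reveal it at low grade. Incidence and severity of TEAEs and laboratory abnormalities are secondary endpoints, and safety at the RP2D is Part B's first secondary objective. In the AESI table, a zero or low diabetes count could mean that the event was rare or that nobody looked. Counts would also not be comparable across the named endocrinopathies, because the intensity of testing differs. With no pre-treatment glucose, a raised value found later has nothing to be compared with. Table 7-2 adds to this by calling for corticosteroids, often at 1 to 2 mg/kg/day, for several other immune-related events, so some hyperglycaemia on study may have another cause.

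**Working it through.** There is no stated figure to reproduce: no sample size, error rate or boundary depends on this. The check is a search of the schedule and a count.

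**1. Where glucose could appear.** I looked in Protocol 8.2.2.5, both schedules with footnotes 2 and 2a to 2f, 8.2.2.6, Table 5-3, Table 7-2, and SAP 18.1.16 and 18.3 to 18.3.3. None lists glucose, HbA1c or urinalysis. On Days 3 and 17 of Cycle 1 (Part A only) the draw is limited to liver tests and creatinine.

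**2. Scheduled full-panel draws for a patient completing 13 cycles (8.2.2.5).**

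| Period | Full-panel draws | With glucose |
|---|---|---|
| Screening | 1 | 0 |
| Cycle 1: Days 8, 15, 22, and Day 1 under stated conditions | 3 or 4 | 0 |
| Cycles 2 and 3: Days 1 and 15 | 2 + 2 = 4 | 0 |
| Cycles 4 to 13: Day 1 | 10 | 0 |
| EOT | 1 | 0 |
| Total | 1 + 3 + 4 + 10 + 1 = 19, or 20 with C1D1 | 0 |

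The C1D1 panel is required only if screening tests were more than 7 days old or eligibility was not met at screening.

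**3. The named endocrinopathies side by side.**

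| AESI | Screening or Day 1 value | Scheduled on treatment |
|---|---|---|
| Thyroid disorders | TSH, FT3, FT4 on C1D1 | C1D15 and Day 1 of every later cycle |
| Adrenal insufficiency | cortisol, ACTH at screening | only if clinically indicated |
| Pituitary disorders | ACTH, cortisol, FSH/LH, sex hormones at screening | only if clinically indicated |
| New-onset type I diabetes | none | none |

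Diabetes is the only row with neither a starting value nor a scheduled repeat.

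**4. Effect on the estimate.** Let p be the true incidence of new-onset cases and s the probability that a case is recognised and flagged. If every flagged case is genuine, the expected reported incidence is s × p, and the relative shortfall is 1 − s. The documents fix neither p nor s. The direction follows from the schedule: with no scheduled test, s depends on symptoms and local habit, and an asymptomatic case may go unseen. The size cannot be computed.

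**5. Effect on the new-onset label.** Known diabetes can be identified from medical and medication history, taken at screening and C1D1, and from concomitant medications, recorded from consent. The AE definition in 9.1.1 asks for change from the condition at the first visit. What stays unresolved is hyperglycaemia that was present but undiagnosed at entry.

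**The case against.** The strongest reply is that this AESI is an investigator's diagnosis, not a laboratory value. Clinically triggered detection is also the protocol's usual approach. Cortisol and ACTH are repeated only if indicated, and so are CPK and troponins, which bear on myositis and myocarditis. AE monitoring is continuous from consent to 5 months after the last nivolumab infusion (unless new anticancer treatment or end-of-life care starts earlier), and examination, vital signs and weight are repeated. Laboratory work is local and nothing bars an unscheduled glucose. A single value does not establish type I diabetes, and samples may be non-fasting: 7.6.1 asks for only 2 hours before dosing. No dose-decision, futility or response rule uses glucose, and the affected output is one line of a descriptive table in a single-arm study.

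Most of this stands, and it rules out several stronger readings that a reader might infer:

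- **That no glucose is ever measured, or that low-grade cases cannot be detected.** The documents support only that no test is scheduled.
- **That coverage of this AESI is nil for all patient time.** That ignores continuous AE monitoring.
- **That a detected case cannot be called new.** Known diabetes is on record, so the ambiguity is confined to undiagnosed disease at entry.
- **That diabetes alone lacks scheduled on-treatment testing.** Adrenal, pituitary and cardiac AESIs lack it too, but they have a screening value.

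Two things survive: diabetes has no baseline value, and its detection depends on unscheduled testing that may vary by site. Retained PK samples may be used for retrospective safety tests (8.2.3), but that is optional, and the protocol does not say whether glucose would be valid in them.

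**Conclusion.** The point holds in limited form. A named AESI of any grade has no scheduled glucose, HbA1c or urinalysis: 0 of 19 or 20 full-panel draws over 13 cycles, including screening. Its reported incidence is a lower bound with a shortfall of unknown size, and undiagnosed pre-existing hyperglycaemia cannot be reliably separated from new onset.

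This rests on two assumptions. First, the laboratory list in 8.2.2.5 is exhaustive for scheduled tests, which the matching footnotes support. Second, flagged cases are genuine new-onset diabetes; if pre-existing or steroid-related hyperglycaemia were flagged as the AESI, the error could run the other way, and the missing baseline makes that harder to exclude. The primary endpoints are not affected. The change is worth making because it improves safety ascertainment for very little effort.

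**What to change.** Add blood glucose, with fasting status recorded, to the chemistry panel in Protocol 8.2.2.5 and to footnote 2c of Tables 1-1 and 8-6. Measure it on the samples already drawn at screening, each full-panel safety visit and EOT. Include it in the SAP 18.3 laboratory summaries, presented as supportive data beside the investigator-diagnosed AESI and not as a substitute for it.

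SAP 5.0 (section 4.3) already refers to futility of the Part B cohorts, so sampling may be over. If it is, state in the report that the diabetes AESI count rests on unscheduled detection and is a lower bound, and that no baseline glucose was scheduled.

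The cost is one extra local analyte plus protocol, eCRF and SAP wording, with no added visit or draw. The downside is some non-specific hyperglycaemia, from non-fasting samples or steroids, which the investigator must attribute.
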